6.5.8 Subgroups of Interest for safety

The following factors are medically important subgroups for safety analysis: Race, smoking status, BMI category, NAFLD, and NASH. The data are being analyzed by subgroup are as follows:

- \circ Age (< 55 years, \geq 55 years): Treatment emergent AE (TEAE) table by SOC and PT, and Categorical Liver function table
- Race 1 (White, Non-White): Treatment emergent AE (TEAE) table by SOC and PT, and Categorical Liver function table
- Race 2 (White, Black, Asian, Other): Treatment emergent AE (TEAE) table by SOC and PT, and Categorical Liver function table
- Race 3 (Black, Non-Black): Treatment emergent AE (TEAE) table by SOC and PT, and Categorical Liver function table
- Geographical region (Europe, North American): Treatment emergent AE (TEAE) table by SOC and PT, and Categorical Liver function table

- Smoking Status(current, former/never, per substance use tabacco history CRF page): Treatment emergent AE (TEAE) table by SOC and PT, and Categorical Liver function table
- BMI category (>=18.5 kg/m² to <25 kg/m², >=25 kg/m² to <30 kg/m², >=30 kg/m²): Treatment emergent AE (TEAE) table by SOC and PT, and Categorical Liver function table
- Isolated non-alcoholic fatty liver disease (NAFLD) (Yes, No, per targeted medical history CRF page): Categorical liver function table
- Non-alcoholic steatohepatitis (NASH) (Yes, No, per targeted medical history CRF page): Categorical liver function table
- Diabetic Status (Yes, No): Categorical liver function table

6.6 Analysis of Pharmacokinetics

The statistical methods for PK data will be described in a separate analysis plan. Results of the population PK analysis will not be reported in the Clinical Study Report but in a separate population PK report.

Plasma concentration of fezolinetant and ES259564 will be listed.

6.6.1 Estimation of Pharmacokinetic Parameters

All details of the population PK analysis will be described in a separate analysis plan.

6.7 Analysis of Pharmacodynamics

Serum concentrations of sex hormones [luteinizing hormone (LH), follicle-stimulating hormone (FSH), estradiol (E2), Testosterone Total/Free, Androstenedione, dehydroepiandrosterone (DHEA), Estrone] and sex hormone-binding globulin (SHBG) will be summarized using descriptive statistics (number of subjects, mean, SD, median, minimum and maximum) for each visit and time point and for change from the baseline to each postdose visit, if the data is available.

6.8 Other Analyses

Not applicable.

6.9 Interim Analysis (and Early Discontinuation of the Clinical Study)

There will be no interim analysis.

6.10 Additional Conventions

6.10.1 Analysis Windows

Study Day for analysis windows will be calculated as date of visit/assessment – first dose date +1.

Study Day for the follow-up (FUD) phase will be calculated as date of visit/assessment – last dose date of study treatment (Date of EOT).

Except for adverse events, for the analysis window (weeks prior to the follow-up period), the last day is always 1 day after the last day of exposure to double-blind treatment.

The end of overall treatment is defined as the last day of treatment +1 and the follow-up period begins at last overall treatment + 2 days and onward (Follow-up Study Day 2).

The data summary by visits will be done following the analysis windows specified in the table below:

Analysis	Scheduled	Analysis Windows (day)				
Visits	Day in Protocol	a)	b)	c)	d)	e)
Baseline	Day 1	Last non-missin	ng value on or prio	or to day 1 (inclu	sive)	
Week 2	Day 15	2 to 22				
Week 4	Day 29	23 to 43	2 to 43	2 to 57		
Week 8	Day 57	44 to 71	44 to 71			
Week 12	Day 85	72 to 99	72 to 99	58 to 127	2 to 127	
Week 16	Day 113	100 to 127	100 to 127			
Week 20	Day 141	128 to 155	128 to 155			
Week 24	Day 169	156 to 183	156 to 183	128 to 267	128 to 267	
Week 28	Day 197	184 to 211	184 to 211			
Week 32	Day 225	212 to 239	212 to 239			
Week 36	Day 253	240 to 267	240 to 267			
Week 40	Day 281	268 to 295	268 to 295			
Week 44	Day 309	296 to 323	296 to 323			
Week 48	Day 337	324 to 351	324 to 351			
Week 52	Day 365	352 to 376	352 to 376	268 to 376	268 to 376	2 to 376
Follow-up	Day 386	Last treatment + 2 days and onwards				

a) Apply to Clinical laboratory and urinalysis

b) Apply to Vital signs

- c) Apply to Blood PD/PK sample, EQ-5D-5L, MENQoL
- d) Apply to C-SSRS
- e) Apply to 12-lead ECG

For TVU and DXA, the week 52 analysis window is day 2 to last treatment + 30 days. For endometrial biopsy, refer to Section 6.5.5 for analysis window.

As a general rule, if more than one observation exists within the analysis window, the observation closest to the scheduled visit day will be selected for that visit. If there are two observations that have the same distance from the scheduled day, the value that is after the scheduled day will be selected in the analysis. If more than one observation is made on the same day, an average value if continuous or the worst value if categorical will be included in the analysis.

The Follow Up visit (Week 55) will include all data collected beyond 1 day after the last dose of the study drug. If there are more than one value, then the value that is closest to Day 386 from the last dose of study drug will be selected for the analysis. The same logic will be applied as in above for more than one value.

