- p. For practical reasons, the timing of DXA may vary from the actual time of the visit, depending on the DXA availability (DXA appointment). The screening visit (days -35 to -1 [visit 1]) DXA can be performed once the subject has been deemed eligible based on screening laboratory tests, or at visit 2 but must be performed before randomization. The week 52 (visit 15) DXA should be performed between week 50 and week 52, inclusive. For subjects who are withdrawn from the study prior to completion, a DXA will be completed as soon as possible after study drug discontinuation (preferably within 2 weeks).
- q. For HBsAG, anti-HCV antibodies, anti-HBs antibodies, anti-HBc antibodies and anti-HIV antibodies.
- r. Pharmacodynamic samples will be taken predose (1 hour) at day 1 (visit 2), week 4 (visit 3), week 12 (visit 5), week 24 (visit 8), at week 52 (visit 15) and week 55 (visit 16). Markers include LH, FSH, E2, SHBG, androstenedione, dehydroepiandrosterone, estrone and testosterone.
- s. Pharmacokinetic samples to be taken predose at week 4 (visit 3), week 12 (visit 5), week 24 (visit 8), and at EOT/ED week 52 (visit 15) and at 1 to 3 hour postdose at week 4 (visit 3). A predose sample will be collected for any subject with a signal of elevated ($> 3 \times$ ULN) transaminases. For the week 52 (visit 15) PK/PD samples, the last dose of study drug should be administered the day prior to the week 52 (visit 15) visit. Sites should collect week 52 (visit 15) PK/PD samples approximately at the same time when study drug would typically be given on site.
- t. A clinician will administer the C-SSRS measure electronically at the clinic visit, prior to any invasive procedures. This will be administered electronically via the site tablet at screening, (visit 1), week 0 (visit 2), week 12 (visit 5), week 24 (visit 8), EOT/ED week 52 (visit 15) and the follow-up visit (week 55 [visit 16]).

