- Safety laboratory tests collected at a local lab including biochemistry, hematology, liver biochemistry and coagulation panel testing.
- Home healthcare services may be available in cases where arrangements are made in advance by the site upon request from the subject(s)

Due to the nature of the Screening (visit 1), Randomization, week 0 (visit 2) and EOT/ED week 52 (visit 15) visits, which include important study procedures, these visits must be conducted in the clinic. All other visits during the COVID-19 pandemic may be conducted utilizing all or some of the following services: home healthcare, telemedicine conferences (telephone visits) or safety laboratory tests collected at a local laboratory.

Subjects who screen failed due to the COVID-19 pandemic study suspension and have a documented evaluable endometrial biopsy from the original screening period do not have to undergo a repeat biopsy should they decide to rescreen.

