Urine pregnancy test	Visit collection of samples at local facility acceptable if results can be made available to investigative site. To be completed at local laboratory.	Please refer to protocol schedule of assessments.									
Clinical laboratory	Visit collection of samples at local facility acceptable if results can be made available to investigative site. To be completed at local laboratory.	Please refer to protocol schedule of assessments.									
Serology	Visit collection of samples at local facility acceptable if results can be made available to investigative site. To be completed at local laboratory.	Please refer to protocol schedule of assessments.									
Blood pharmacodynamic sample	Delay the measurements to subsequent visit.	Please refer to protocol schedule of assessments.									
Blood pharmacokinetic sample	Delay the measurements to subsequent visit.	Please refer to protocol schedule of assessments.									

Table continued on next page

Assessments	Alternate Approaches	Treatment Period									Follow-up Visit
		Visit 2b	Visit 3	Visit 4	Visit 5	Visit 6	Visit 7	Visit 8	Visits 9, 10, 11, 12, 13 and 14	Visit 15/ EOT/ED	
Study Visit											
Time of Visit		Week 2	Week 4	Week 8	Week 12	Week 16	Week 20	Week 24	Weeks 28, 32, 36, 40, 44 and 48	Week 52	Week 55
Visit days		Day 15	Day 29	Day 57	Day 85	Day 113	Day 141	Day 169	Day 197, 225, 253, 281, 309 and 337	Day 365	Day 386
Visit Window (days)		± 3	± 3	± 3	± 3	± 3	± 3	± 3	± 3	-14 /+ 6	± 3
C-SSRS	Remote/Virtual/Telemedicine Visits allowed	Please refer to protocol schedule of assessments.									
EQ-5D-5L	Remote/Virtual/Telemedicine Visits allowed for non-dosing visits	Please refer to protocol schedule of assessments.									
MENQoL	Remote/Virtual/Telemedicine Visits allowed for non-dosing visits	Please refer to protocol schedule of assessments.									
ePRO training	Remote/Virtual/Telemedicine Visits allowed for non-dosing visits	Please refer to protocol schedule of assessments.									
Dispense study drug	Patients can be brought into the clinic earlier to provide additional study drug. Courier service directly to patient allowed.	Please refer to protocol schedule of assessments.									
Study drug compliance and accountability	Patients can be brought into the clinic earlier to provide additional study drug. Courier service directly to patient allowed.	Please refer to protocol schedule of assessments.									

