6.5 Analysis of Safety

Overall long-term safety of fezolinetant and the effect of fezolinetant on endometrial health will be the primary objective of this study. The safety assessments include adverse events, laboratory assessments, vital signs, C-SSRS, ECG, endometrial health assessment and imaging (mammogram, DXA, TVU). In all analysis of safety, the treatment group includes placebo, fezolinetant 30mg, fezolinetant 45mg and fezolinetant total will be presented by treatment group for SAF, unless specified otherwise. For analyses by visit, the analysis windows from Section 6.10.1 will be applied. Except for adverse events and follow-up visit data, only data up to one day after the last dose date will be considered for the analyses.

The baseline value for safety endpoint will be the last non-missing value taken on or prior to first dose of study drug unless otherwise noted.

Primary Safety Variables

- Frequency and severity of AEs.
- Percentage of subjects with endometrial hyperplasia.
- Percentage of subjects with endometrial cancer.

Secondary Safety Variables

- Change from baseline in endometrial thickness at 12 months.
- Percentage of subjects with disordered proliferative endometrium.
- Change from baseline in bone mass density (BMD) and trabecular bone score (TBS) at hip and spine at 12 months.
- Change from baseline to each timepoint in vital signs: sitting systolic and diastolic blood pressure and pulse rate.

- Change from baseline to each timepoint in laboratory tests: hematology, biochemistry and urinalysis.
- C-SSRS at each timepoint.
- Change from baseline to each timepoint in ECG parameters

Exploratory Safety Variables

- Change from baseline to specified time points in serum concentrations of sex hormones and sex hormone-binding globulin (SHBG) (week 4, 12, 24, 52 and 55).
- Plasma concentration of fezolinetant and the fezolinetant metabolite ESN259564 at specified timepoints (week 4, 12, 24 and 52).

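### SAP 6.10.1 gives two different ends for the Week 52 window; read by its table, a Visit 15 on Day 377 or later in a woman still dosing belongs to no analysis visit

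*SAP*

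**What the plan says.** SAP 6.10.1 bounds the on-treatment windows in two ways.

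- **In the text.** For everything except adverse events, in the weeks before follow-up, "the last day is always 1 day after the last day of exposure to double-blind treatment". SAP 6.5 has a matching rule for safety data other than adverse events and follow-up visits: "only data up to one day after the last dose date will be considered for the analyses".
- **In the table.** By-visit summaries are to follow a table whose Week 52 row ends at Day 376 in all five columns: Days 352 to 376 for laboratory tests and for vital signs, 268 to 376 for PD/PK samples and the two questionnaires, 268 to 376 for C-SSRS, and 2 to 376 for ECG.

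Follow-up is defined from the last dose and not from a study day. The table gives it as "Last treatment + 2 days and onwards", and the text adds that the Week 55 visit "will include all data collected beyond 1 day after the last dose of the study drug".

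In the protocol, Table 1 schedules Visit 15 on Day 365 with a window of -14/+6 days. Footnote s to that table, on the Week 52 PK/PD samples, says that "the last dose of study drug should be administered the day prior to the week 52 (visit 15) visit". Table 1 schedules the 12-lead ECG only at screening and at Visit 15/EOT/ED.

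**The concern.** The two ends agree only when the last dose is on Day 375. If the last dose is earlier, the last-dose rule is the tighter limit and Day 376 does nothing. If it is later, data from Day 377 up to last dose + 1 day are on-treatment by the text, past the end of Week 52 by the table, and too early for follow-up. A Visit 15 run as footnote s describes falls on last dose + 1 day, so a sufficiently late one lands in that gap.

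ECG has most at stake. SAP 6.5.4 tabulates ECG variables and QTc categories by treatment visit, and an affected woman has no other scheduled post-baseline ECG. If she happened to have an unscheduled ECG at any time from Day 2 to Day 376, that reading would stand as her Week 52 value in place of the Visit 15 one. Week 52 questionnaire, hormone, C-SSRS, vital-sign and laboratory values would also leave the by-visit outputs.

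The situation is possible in this trial. During COVID-19 site closures the protocol says of Visits 1, 2 and 15, "which include important study procedures, these visits must be conducted in the clinic". The SAP itself expects some visits outside the protocol window (6.5.2.1) and has an exposure category above 365 days (6.3).

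**Working it through.** **Inputs.** Scheduled days 169, 337, 365 and 386 and the Visit 15 window of -14/+6 days (Protocol Table 1). Week 52 limits, last dose + 1 day cap and follow-up start (SAP 6.10.1).

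**Step 1. Reproduce the table's limits.** They are midpoints between consecutive scheduled days for each assessment.

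- Laboratory tests and vital signs, Week 48 to Week 52: (337 + 365)/2 = 351, so Week 52 starts on Day 352.
- PD/PK, questionnaires and C-SSRS, Week 24 to Week 52: (169 + 365)/2 = 267, so Week 52 starts on Day 268.
- All columns, Week 52 to follow-up: (365 + 386)/2 = 375.5, rounded up to 376.

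Day 376 is therefore the midpoint between Visit 15 and the scheduled follow-up visit. Because follow-up is assigned from the last dose, that midpoint does not separate the two visits.

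**Step 2. Compare with the protocol window.** Visit 15 may fall from 365 - 14 = Day 351 to 365 + 6 = Day 371. The first day outside the Week 52 row is Day 377, which is 377 - 365 = 12 days after the scheduled day and 377 - 371 = 6 days past the protocol window.

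**Step 3. Classify the visit.** Let d be the day of Visit 15 and L the day of the last dose.

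- Follow-up if d ≥ L + 2.
- Week 52 if d is at or above the lower limit, d ≤ 376 and d ≤ L + 1.
- No analysis visit if d ≥ 377 and d ≤ L + 1, which requires L ≥ 376.

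| Visit 15 on | Last dose same day | Last dose 1 day before | Last dose 2 days before |
|---|---|---|---|
| Day 371 | Week 52 | Week 52 | Follow-up |
| Day 372 | Week 52 | Week 52 | Follow-up |
| Day 376 | Week 52 | Week 52 | Follow-up |
| Day 377 | none | none | Follow-up |
| Day 380 | none | none | Follow-up |
| Day 386 | none | none | Follow-up |
| Day 390 | none | none | Follow-up |

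If dosing stopped on Day 364 or 365, a Visit 15 on Day 371, 376, 377 or 380 is follow-up, so it is assigned.

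**Step 4. Apply the alternative limit.** With last dose + 1 day in place of 376, every entry marked none becomes Week 52. No other entry changes.

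**Step 5. Trace the outputs for an affected woman.**

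| Lost, read by the table | Kept |
|---|---|
| Week 52 rows for laboratory tests, vital signs, hormones and C-SSRS | Primary liver threshold table: highest value to last dose + 1 day (SAP 6.5.2.1) |
| Week 52 MENQOL and EQ-5D-5L values, including the Week 52 records in the MMRM (earlier visits still contribute) | Laboratory shifts to the worst finding in the treatment period (SAP 6.5.2) |
| Visit 15 reading in all ECG and QTc tables | Adverse events; TVU, DXA and biopsy, which have their own windows; listings |

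**The case against.** The best defence is that the sentence containing "the last day is always 1 day after the last day of exposure to double-blind treatment" already closes the gap. It can be read as setting the end of the last on-treatment window, with follow-up starting the next day, so that the two periods are contiguous and 376 is only nominal. That reading is reasonable, but the SAP does not say that the sentence overrides the table, and it directs by-visit summaries to the table. On this reading the printed 376 is wrong; on the other, data are lost. Two programmers could produce different outputs, so the conflict stands.

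The defence is stronger on likelihood and reach. A reader might infer three things that the documents do not support.

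- **That COVID-19 rules force Visit 15 to be late with dosing continuing.** The clinic-only rule does not mean that the visit can only be delayed, since the window allows it up to 14 days early. The crisis appendix does say "Courier service directly to patient allowed", but that row refers back to the normal schedule, which last dispenses at Visits 9 to 14. Planned treatment is 52 weeks, and no passage provides for dosing to Day 376. Footnote s ties the last dose to the visit, so longer dosing can happen, but it is not planned.
- **That the woman's data are dropped altogether.** Step 5 shows otherwise. No primary endpoint is touched, nor are endometrial thickness, BMD or TBS. A clinically significant ECG, laboratory or vital-sign abnormality is reportable as an adverse event (Protocol 5.8.1.1), and adverse events are exempt from the windows.
- **That a material share of each arm is affected.** The documents give no frequency of late, on-drug Visit 15s, so any percentage would be invented. An exposure category above 365 days does not imply exposure to Day 376.

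**Conclusion.** The point holds as an internal conflict in SAP 6.10.1, and it is minor. On the table's wording, an on-drug Visit 15 on Day 377 or later has no analysis visit. The consequence is confined to by-visit Week 52 summaries, the Week 52 part of the exploratory MMRM, and the ECG and QTc tables. No visit within the protocol window is lost, and Days 372 to 376 are also covered.

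The conclusion assumes that the table governs over the sentence above it, and that dosing continues to Day 376 or later, with the last dose on the day of Visit 15 or the day before. How many women meet that condition cannot be derived from the documents; the number is probably small. A reader might also describe them as the longest-exposed women, which is true by construction, but the difference is a matter of days (about 12 or more beyond a 52-week course) and does not raise the severity.

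**What to change.** In the Week 52 row of the SAP 6.10.1 table, replace the upper limit of 376 by last dose + 1 day in columns a to e. Keep the present lower limits and the rule that the observation closest to the scheduled day is selected, so that an on-time value is still preferred over a late one. Add a footnote giving the range of actual study days in the Week 52 summaries. Table and text then agree, and Week 52 and follow-up meet without a gap.

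The cost is one row of the table, changed before database lock. The only downside is that a few Week 52 values may be later than Day 376, which the footnote makes visible.

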5.5.2 Dual-Energy X-Ray Absorptiometry (DXA)

Changes in BMD and TBS of hip and spine will be assessed by dual-energy X-ray absorptiometry (DXA) scan at screening (visit 1) and at week 52/EOT (visit 15).

The central DXA reader vendor will provide instructions for performing the DXA scans. The results will be transferred to the central DXA reader vendor, who will ensure that all data will be analyzed in the same way and will be blinded to the treatment allocation.

For practical reasons, the timing of DXA may vary from the actual time of the visit, depending on the DXA availability (DXA appointment). The screening visit (days -35 to -1 [visit 1]) DXA can be performed once the subject has been deemed eligible based on screening laboratory tests, or at visit 2, but must be performed before randomization. The week 52 (visit 15) DXA should be performed between week 50 and week 52, inclusive. For

subjects who are withdrawn from the study prior to completion, a DXA will be completed as soon as possible after study drug discontinuation (preferably within 2 weeks).

When DXA imaging is received, it goes through a quality control (QC) process to make sure the imaging parameters required for image review and assessment have been met. For TBS to be calculated, the DXA imaging is processed and analyzed as it would normally be and then evaluated using an automated algorithm to determine the TBS. TBS is a bone texture assessment that serves as a substitute for bone microarchitecture [Muschitz et al, 2015] and predicts fracture risk independent of BMD and clinical risk factors [McCloskey et al, 2016].

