2 STUDY OBJECTIVE(S) AND DESIGN

2.1 Study Objective(s)

Primary Objective

- To evaluate the long-term safety and tolerability of fezolinetant in women seeking treatment for relief of Vasomotor Symptoms (VMS) associated with menopause.
- To evaluate the effect of fezolinetant on endometrial health after long-term treatment in women seeking treatment for relief of VMS associated with menopause.

Secondary Objective

• To evaluate the effect of fezolinetant on bone mineral density after long-term treatment in women seeking treatment for relief of VMS associated with menopause.

Exploratory Objectives

- To evaluate the effect of fezolinetant on subject-reported quality of life measures.
- To evaluate the pharmacokinetics of fezolinetant and its metabolite, ESN259564.

[figure not shown]

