5.2 Secondary Safety Endpoints

The secondary endpoints are:

- Change from baseline in endometrial thickness at 12 months.
- Percentage of subjects with disordered proliferative endometrium.
- Change from baseline in bone mass density (BMD) and trabecular bone score (TBS) at hip and spine at 12 months.
- Vital signs: sitting systolic and diastolic blood pressure and pulse rate.
- Laboratory tests: hematology, biochemistry and urinalysis.
- C-SSRS.
- ECG parameters.

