6.5.5 Endometrial Health Assessment

Ultrasound results (endometrial thickness) will be summarized using mean, standard deviation, minimum, maximum and median by treatment group and visit. The within-subject change will be calculated per visit as the post-baseline measurement minus the baseline measurement and summarized by treatment group and visit. For change from baseline in endometrial thickness, an ANCOVA model, with treatment and strata smoking status (current vs former/never) as factors, with baseline weight and baseline value as covariates, will be used for treatment comparisons.

The descriptive reasons for not evaluable biopsy will be summarized. It includes reasons of not done from eCRF page, reasons of not done from lab and pathologiest readings.

For all postbaseline biopsies, the concordance of 2 of the 3 pathologists reviews will be accepted as the final diagnosis. If there is no agreement among the three pathologists, the most severe diagnosis will then be used as the final diagnosis.

The satisfactory endometrial biopsy results will be summarized for the endometrial health set (EH set). EH set consists of all subjects who are randomized and receive at least one dose of study drug, had the postbaseline biopsy done within 30 days after the last dose of study drug, and

- had an acceptable biopsy at Baseline (at least one endometrial biopsy with satisfactory tissue and no read of hyperplasia, disordered proliferative pattern or malignant); and
- had an satisfactory endometrial biopsy result after or on Day 326 or had a postbaseline final diagnosis of hyperplasia, disordered proliferative or malignant prior to Day 326.

Baseline biopsy is the last non-missing value on or prior to first dose of study drug. When more than one biopsy results are present at postbaseline, if no final diagnosis of hyperplasia, disordered proliferative pattern or malignant, the last non-missing satisfactory result within the window will be counted; otherwise, the more severe result will be counted. For percentage of subjects with final diagnosis of endometrial hyperplasia, percentage of subjects with endometrial cancer, and percentage of subjects with disordered proliferative endometrium, the exact (Clopper-Pearson) upper one sided 95% confidence interval will be provided.

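### SAP 6.10.1 counts any DXA or ultrasound from Day 2 as Week 52, so women with only an early scan enter the 12-month bone and endometrial-thickness analyses

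*SAP*

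**What the plan says.** The SAP's only secondary objective is "To evaluate the effect of fezolinetant on bone mineral density after long-term treatment". Among the secondary endpoints in SAP 5.2 are "Change from baseline in bone mass density (BMD) and trabecular bone score (TBS) at hip and spine at 12 months" and "Change from baseline in endometrial thickness at 12 months".

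Protocol 5.5.2 times the scheduled scan: "The week 52 (visit 15) DXA should be performed between week 50 and week 52, inclusive". For women withdrawn early, the same section says "a DXA will be completed as soon as possible after study drug discontinuation", preferably within two weeks. Protocol 5.5.3 requires an ultrasound at the early-discontinuation visit, and footnote m of the Schedule of Assessments adds one for uterine bleeding on treatment.

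SAP 6.10.1 then sets the analysis window: "For TVU and DXA, the week 52 analysis window is day 2 to last treatment + 30 days". If several scans fall in it, the one closest to the scheduled day is used.

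The ANCOVAs in SAP 6.5.5 (thickness) and 6.5.6 (BMD, TBS) contain treatment, smoking status, baseline weight and baseline value. The one bone sensitivity analysis adds women with no post-baseline value, at zero change.

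For biopsies the SAP does set a time limit. Unless there is an earlier abnormal final diagnosis, a woman counts in the endometrial health set only if she "had an satisfactory endometrial biopsy result after or on Day 326".

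**The concern.** The label and the content of the window disagree. A value called Week 52 may come from any time after the first day of dosing, while the endpoint is a change at 12 months and the objective concerns long-term treatment. The protocol's own early-discontinuation rule guarantees that some early scans will exist.

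An effect on bone would be expected to accumulate with exposure. Scans taken after a few weeks would then carry only part of it, and averaging them with true 12-month scans understates the difference from placebo. In a safety comparison, a bias toward no difference is the unfavourable direction. As planned, nothing in the report would let a reader separate the 12-month result from this mixture.

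**Working it through.** **1. Is there a plan figure to reproduce?** Not on this point. The SAP gives no power, SD, margin or expected effect for BMD, TBS or thickness, and no 52-week discontinuation rate. Its sample-size figures concern event counts and the hyperplasia rate. They reproduce by exact binomial calculation (for example 1 − 0.999^580 = 44.03%) and do not depend on this window.

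**2. Who is affected?**
- A woman with scans at Day 40 and Day 360 contributes Day 360, which is closer to Day 365. No effect.
- A woman who takes her last dose on Day 28 and is scanned on Day 40 is inside the window (Day 40 is 12 days after last dose, and the limit is 30). With no later scan, she contributes a Week 52 value after about 4 weeks of drug.
- A bleeding-triggered ultrasound counts only if no ultrasound closer to Day 365 exists in the window.

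**3. Does anything else in the plan correct for it?** Neither ANCOVA has a term for scan time or exposure. No analysis is limited to late scans. The zero-change analysis leaves women with an early scan as they are, since they have a post-baseline value, and it also pulls toward no difference.

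**4. Size, under stated assumptions.** Let D be the true 12-month arm difference, e the share of analysed women with only an early scan, and f the fraction of the year elapsed at that scan. With linear accrual, and e and f equal across arms:

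expected estimate = (1 − e)D + e·f·D = D[1 − e(1 − f)]

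| e (assumed) | f = 0.25 | f = 0.5 |
|---|---|---|
| 10% | 1 − 0.10 × 0.75 = 0.925 | 1 − 0.10 × 0.5 = 0.950 |
| 19% | 1 − 0.19 × 0.75 = 0.858 | 1 − 0.19 × 0.5 = 0.905 |

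The 19% is borrowed from the 12-week phase 2b study in Protocol 2.2.2 (81% completed). It is a reference value, not an estimate for this trial.

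**5. If accrual is not linear.** Suppose the effect saturates with an 8-week half-time: g(w) = (1 − 2^(−w/8)) / (1 − 2^(−52/8)). Then g(12) = 0.654 and g(26) = 0.905. At e = 19% the retained share is 1 − 0.19 × 0.346 = 0.934 for week-12 scans and 1 − 0.19 × 0.095 = 0.982 for week-26 scans. The dilution is smaller.

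**6. If the arms differ in e.** Let the true 12-month changes be A (active) and P (placebo). The estimate becomes A[1 − e_A(1 − f_A)] − P[1 − e_P(1 − f_P)], which is no longer simple attenuation. As an illustration, take the phase 2b non-completion rates (fezolinetant 20%, placebo 16%) as e, with f = 0.25 and the same true loss L in both arms. The result is 0.85L − 0.88L = −0.03L, so the fezolinetant arm would appear to lose 3% of L less bone although the true losses are equal.

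**7. What a Day 326 lower bound would do.** Under linear accrual by scan time, each admitted scan carries at least 326/365 = 89% of the 12-month effect. Measured by dosing, a Day 326 scan taken 30 days after last dose still implies dosing to Day 296, or 296/365 = 81% of the year.

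**The case against.** The window looks deliberate. The Schedule of Assessments has one post-baseline visit for these scans, combining week 52, end of treatment and early discontinuation. ECG, also scheduled only at screening and that visit, has a Week 52 window of Day 2 to 376. Read this way, the plan uses an end-of-treatment value and keeps treated women who stopped early. A late-scans-only analysis conditions on staying in the trial about 11 months, which is a selection made after randomisation. The Day 326 rule for biopsies defines a denominator for an incidence rate and does not carry over automatically to a change score. All of this stands, and it is why the restricted analysis should be added and not substituted. It does not justify calling a mixed-time value a 12-month change, and the ECG endpoint is not defined at 12 months.

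Two stronger readings are tempting. The first is that early scans dilute any bone or endometrial effect. The documents do not support this for the endometrium: nothing says thickness change accumulates over the year, and a bleeding-triggered ultrasound with no later scan could select thicker endometrium and bias the other way.

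The second is that bone loss could be understated by as much as 30%. That needs e = 40% with f = 0.25 (retained share 0.70), and no source gives 40%. The SAP's allowance of up to 60% without evaluable biopsies includes baseline failures and refusals. The 19% is also weak: it comes from a 12-week study with total daily doses up to 180 mg, against 30 and 45 mg here. The commonest reason for stopping there was withdrawal of consent, and such women may never be scanned.

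Loss of precision is a weaker objection. In a hypothetical comparison with 80% power at 580 per arm, e = 19% and early scans at week 12, power is 66.7% with early scans included and 71.3% with them excluded (470 per arm).

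**Conclusion.** The point holds for women whose only post-baseline scan is early. They enter the 12-month ANCOVA under a Week 52 label, and no planned analysis isolates the 12-month result. Women with a Week 52 scan are protected by the closest-day rule, so a reader should not infer that the window contaminates everyone's value.

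For BMD and TBS the bias is toward zero if change accrues with exposure and if early scans are similarly common and similarly timed across arms. If they are not, the error need not be simple attenuation. For endometrial thickness the direction is uncertain.

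Confidence in the mismatch is high. Confidence in its size is low: a retained share of 86–95% is an illustration under assumed e, assumed f and linear accrual, and a saturating effect would lose less. These are secondary safety endpoints with no stated margin, so this is a correction the SAP should make and not a threat to the primary analysis.

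**What to change.** In SAP 6.10.1, 6.5.5 and 6.5.6:

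1. Add a 12-month ANCOVA for BMD, TBS and endometrial thickness restricted to scans from Day 326 (the lower bound already used for biopsies) to last dose + 30 days.
2. Label the current all-scans ANCOVA as an end-of-treatment analysis (last on-study scan), and report both.
3. Tabulate scans before Day 326 separately by arm, with time of scan, so that the shares and timing can be compared.
4. Accompany the restricted analysis with a missing-data sensitivity analysis that does not assume zero change and that includes women with only an early scan. Otherwise those women would be in neither the restricted ANCOVA nor the zero-change analysis. Multiple imputation of the 12-month change, using the early value and its timing, with a range of offsets in the fezolinetant arms, is one way.
5. State that the +30-day rule for ultrasound and DXA overrides the general cut-off of last dose + 1 day in SAP 6.5 and 6.10.1. Read literally, the general rule would discard most early-discontinuation DXAs.

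The cost is SAP wording and one extra table per endpoint, plus the sensitivity analysis. The restricted analysis has fewer women and may reflect completer selection, which is why both versions should be reported.
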